#### No:

The time course between the occurrence or worsening of the AE and underlying disease, other medical conditions, or concomitant medications rules out a causal relationship and another cause is suspected.

#### Yes:

The time course between the occurrence or worsening of the AE and the underlying disease, other medical conditions, or concomitant medications is consistent with a causal relationship.

The following factors should also be considered:

- Temporal sequence from treatment with the study drug.
- Preclinical and prior clinical data regarding whether a particular AE could be an effect of the study drug (or class of drug).
- Pharmacology and PK of the investigational product.

An unexpected AE is an experience not previously reported or an AE that occurs with specificity, severity, or frequency that is not consistent with the current selpercatinib IB.

## **9.4 Serious Adverse Event Reporting**

An SAE is any untoward medical occurrence that, at any dose:

- Results in death.
- Is life-threatening.
- Requires hospitalization or prolongation of existing hospitalization.
- Results in disability/incapacity.
- Is a congenital anomaly/birth defect.
- Is an important medical event.

Medical or scientific judgment should be exercised in deciding whether reporting is appropriate in other situations, such as important medical events that may not be immediately life-threatening or result in death or hospitalization but may jeopardize the patient or may require medical or surgical intervention to prevent one of the other outcomes listed in the above definition. These should also be considered serious.

Any hospital admission with at least one overnight stay will be considered an inpatient hospitalization. An emergency room visit without hospital admission will not be recorded as an SAE under this criterion, nor will hospitalization for a procedure scheduled or planned before signing of the informed consent. However, unexpected complications and/or prolongation of hospitalization that occur during elective surgery should be recorded as AEs and assessed for seriousness. Admission to the hospital for social or situational reasons (i.e., no place to stay, live too far away to come for hospital visits) will not be considered inpatient hospitalizations.

In the event of an accidental or intentional overdose by a patient, the site staff must immediately inform Medpace Clinical Safety. The eCRF must be updated to reflect this information. In the event that the overdose is associated with an SAE, the two events should be linked. In the event of an AE associated with an overdose, an SAE report form must be completed detailing the AE and the overdose details.

Disease progression (PD) is an efficacy finding and will not be reported as an AE or an SAE.

### **9.4.1 Serious Adverse Event Reporting – Procedures for Investigators: Initial Report**

All SAEs occurring from the time informed consent is signed through 28 days after the last dose must be reported to Medpace Clinical Safety within 24 hours of the knowledge of the occurrence (this refers to any AE that meets any of the aforementioned serious criteria). All SAEs that the Investigator considers related to study drug occurring after the 28-day follow-up period must be reported to the Sponsor.

To report the SAE, complete the SAE form electronically in the EDC system for the study. When the form is completed, Medpace Safety personnel will be notified electronically and will retrieve the form. If the event meets serious criteria and it is not possible to access the internet, send an email to Medpace Safety at [[contact]](mailto:[contact]) or call the Medpace SAE hotline (phone number listed below), and fax the completed paper SAE form to Medpace (fax number listed below) within 24 hours of awareness. When the EDC system becomes available, the SAE information must be entered within 24 hours of the system becoming available.

**SAE Regulatory Reporting:**

The sponsor has a legal responsibility to notify both the local regulatory authority and other regulatory agencies about the safety of a study intervention under clinical investigation. The sponsor will evaluate the reported SAEs, including confirmation of relatedness and assessment of expectedness. The sponsor has processes for safety reports for identification, recording, and expedited reporting of SUSARs according to local regulatory requirements. The sponsor will comply with country-specific regulatory requirements relating to safety reporting to the regulatory authority, IRB/IEC, and investigators.

**9.5 Serious Adverse Event Follow-Up**

For all SAEs occurring during the study, the Investigator must submit follow-up reports to the Sponsor regarding the status of the SAE and the patient’s subsequent course until the SAE has

resolved, or until the condition stabilizes or is deemed chronic (in the case of persistent impairment), or the patient dies.

Within 24 hours of receipt of follow-up information, the Investigator must update the SAE form electronically in the EDC system for the study and submit any supporting documentation (e.g., patient discharge summary or autopsy reports) to Medpace Clinical Safety via fax or email. If it is not possible to access the EDC system, refer to the procedures outlined above for initial reporting of SAEs.

## **9.6 Pregnancy Reporting**

If the patient or partner of a patient participating in the study becomes pregnant during the study or within 28 days of discontinuing study drug, the Investigator should report the pregnancy to Medpace Clinical Safety within 24 hours of being notified. Medpace Clinical Safety will then forward the Exposure In Utero form to the Investigator for completion.

A patient becoming pregnant while on study drug will immediately be withdrawn from the study and early termination study procedures will be performed.

The patient or partner should be followed by the Investigator until completion of the pregnancy. If the pregnancy ends for any reason before the anticipated date, the Investigator should notify Medpace Clinical Safety. At the completion of the pregnancy, the Investigator will document the outcome of the pregnancy. If the outcome of the pregnancy meets the criteria for immediate classification as an SAE (i.e., postpartum complication, spontaneous abortion, stillbirth, neonatal death, or congenital anomaly), the Investigator should follow the procedures for reporting an SAE.

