### 6.3.3 *Restricted Concomitant Medications*

Avoid concomitant use of strong and moderate CYP3A inhibitors (refer to [Appendix D](#)) with selpercatinib which increase selpercatinib plasma concentrations, which may increase the risk of selpercatinib adverse reactions, including QTc interval prolongation. If concomitant use of strong and moderate CYP3A inhibitors cannot be avoided, reduce the selpercatinib dosage and monitor the QT interval with ECGs more frequently (refer to the selpercatinib IB).

Avoid coadministration of strong or moderate CYP3A inducers (refer to [Appendix D](#)) with selpercatinib which decrease selpercatinib plasma concentrations. If during the study, patients require initiation of treatment with strong inhibitors or inducers of CYP3A4 for clinical reasons, then the Sponsor should be consulted to determine whether selpercatinib should be stopped, and therefore whether the patient should be removed from the study.

Avoid concomitant use of a PPI, H2 receptor antagonists, or locally acting antacids with selpercatinib. If concomitant use cannot be avoided, the following guidance should be adhered to:

- Take selpercatinib with food when co-administered with a PPI.
- Take selpercatinib 2 hours before ( $\pm$  30 minutes) or 10 hours after ( $\pm$  30 minutes) administration of an H2 receptor antagonist.
- Take selpercatinib 2 hours before ( $\pm$  30 minutes) or 2 hours after ( $\pm$  30 minutes) administration of a locally-acting antacid.

Examples of PPIs are omeprazole (Prilosec®), esomeprazole (Nexium®), lansoprazole (Prevacid®), pantoprazole (Protonix®), rabeprazole (Aciphex®), and dexlansoprazole (Dexilant®) (refer to [Appendix E](#)). Examples of H2 blocking agents are ranitidine (Zantac®), famotidine (Pepcid®), and cimetidine (Tagamet®). Examples of antacids are aluminum hydroxide/magnesium hydroxide/simethicone (Maalox®), and calcium carbonate (TUMS®).

Patients taking these agents are encouraged to record the time of each dose in relationship to each dose of selpercatinib in the dosing diary (inaccurate recording will not be considered a protocol violation).

Coadministration of medications known to prolong QTc should be avoided if possible (refer to [Appendix J](#) for examples).

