### **6.4      *Removal of Patients from Therapy or Assessment***

Patients will be advised that they are free to discontinue study treatment at any time and that they will be followed for survival after discontinuing treatment (see Section 7.7). Over the course of the study, the Investigator and/or the Sponsor should remove a patient from treatment for any of the reasons listed below:

- PD  
**Exception:** Patients with documented PD who are tolerating treatment and, in the opinion of the Investigator, are deriving clinical benefit from continuing study treatment, may continue treatment with prior Sponsor approval. Sponsor approval is not required for continuing selpercatinib treatment upon a subsequent progression, provided that continued benefit to the patient is documented.
- Unacceptable toxicity
- Intercurrent illness compromising ability to fulfill protocol requirements
- Pregnancy

- Requirement for alternative treatment in the opinion of the Investigator, unless such treatment is temporary (e.g., local radiation or surgery for disease that does not meet the definition of PD)
- Significant noncompliance with protocol
- Withdrawal of consent by the patient
- Loss to follow-up
- Death
- Study terminated by Sponsor

At the time a patient discontinues treatment, all safety data normally required at the EOT visit will be obtained if possible, as outlined in Section 7.5. Patients will enter LTFU where they may be required to undergo disease assessments (see Section 7.7).

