## **6.5 Reasons for End of Study**

Reasons for end of study could be:

- Withdrawal of consent by the patient
- Loss to follow-up
- Death
- Study terminated by Sponsor

A clinical trial is to be discontinued or terminated in case of an unacceptable risk, any relevant toxicity, or a negative change in the risk/benefit assessment. This might include the occurrence of AEs which character, severity or frequency is new in comparison to the existing risk profile. In addition, any data deriving from other clinical trials or toxicological studies which negatively influence the risk/benefit assessment might cause discontinuation or termination of the study.

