## **7.7 Long-Term Follow-Up**

After treatment discontinuation, LTFU will occur approximately every 3 months ( $\pm 1$  month) until the patient has withdrawn consent for further participation, is lost to follow-up, has died, or the Sponsor makes a decision to close the study. Assessments may include: subsequent anticancer therapy(ies) and survival status. LTFU may be conducted by phone. For any patient who is lost to follow-up, the study site will attempt to ascertain survival information via public database search. If survival status still cannot be ascertained, patients will be considered lost to follow-up and will be censored appropriately.

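### Sections 9.6 and 6.3.3 take patients off the study where 6.4 and 7.7 only stop treatment and keep them in survival follow-up

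*Protocol*

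**What the plan says.** Two places in the protocol use the word *study*:

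- Section 9.6, on pregnancy: "A patient becoming pregnant while on study drug will immediately be withdrawn from the study and early termination study procedures will be performed". The next paragraph continues: "The patient or partner should be followed by the Investigator until completion of the pregnancy", and "At the completion of the pregnancy, the Investigator will document the outcome of the pregnancy".
- Section 6.3.3, on patients who need a strong CYP3A4 inhibitor or inducer during the study: the Sponsor is consulted to determine "whether selpercatinib should be stopped, and therefore whether the patient should be removed from the study".

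The sections that govern discontinuation use the word *treatment*:

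- Section 6.4 tells patients that "they will be followed for survival after discontinuing treatment". It then states that "the Investigator and/or the Sponsor should remove a patient from treatment for any of the reasons listed below". Pregnancy is on that list, and the section closes by sending patients who discontinue treatment into LTFU.
- Section 7.7, repeated in section 3.3, runs LTFU "until the patient has withdrawn consent for further participation, is lost to follow-up, has died, or the Sponsor makes a decision to close the study". It covers survival status and subsequent anticancer therapy and may be done by phone.
- Section 6.5 has its own list, introduced by "Reasons for end of study could be", of withdrawal of consent, loss to follow-up, death and termination by the Sponsor.

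In the SAP, section 4.2 reports treatment disposition and study disposition separately. Section 4.3.10 censors OS at the date the patient was last known to be alive.

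**The concern.** Stopping drug and leaving the study are different events, and the SAP reports them separately. A patient who stops drug still contributes survival time through LTFU. A patient who leaves the study does not.

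The sentence in 9.6 is mandatory and leaves no discretion. A site cannot both withdraw a patient from the study and keep her in LTFU. In 6.3.3, the word *therefore* makes leaving the study follow from stopping drug, and 6.4 does not make that link for the reasons it lists.

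What is at stake is completeness of OS and of the record of later anticancer therapy, which section 8.5.2 of the protocol says will be summarised. There may also be some informative censoring. Kaplan-Meier estimation assumes that censoring is unrelated to prognosis, and a patient who needs a strong CYP3A4 drug may need it because of a change in clinical condition. Section 9.6 also calls for early termination procedures, a term the protocol does not define. Its named visits are End of Treatment (EOT, 7.5), Safety Follow-Up (SFU, 7.6) and LTFU (7.7).

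**Working it through.** The point rests on no stated sample size, power or event count, so the check compares the passages.

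**Pregnancy**

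1. Under 6.4, the patient comes off treatment and enters LTFU.
2. Under 7.7 and 3.3, LTFU continues until consent withdrawal, loss to follow-up, death or study closure. Pregnancy is none of these.
3. Under 9.6, the same patient is withdrawn from the study at once.
4. Steps 2 and 3 cannot both be followed. The contradiction stands without 6.5, whose list is not worded as exhaustive and so adds only weak support.

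**Strong CYP3A4 inhibitor or inducer**

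1. Under 6.3.3, the Sponsor is consulted. The same section also describes a patient remaining on drug when an inhibitor cannot be avoided, so removal is not automatic.
2. If the Sponsor decides to stop drug, 6.3.3 links that decision to leaving the study.
3. Under 6.4 and 7.7, a patient who stops drug enters LTFU, and starting such a drug is not a ground for ending it.
4. The conflict therefore arises only after a decision to stop drug.

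**Effect on OS**

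A patient withdrawn from the study has no further LTFU contact. Under SAP 4.3.10 she is censored at the date last known alive, which would be at or near withdrawal. All survival time after that date is missing for her, although 7.7 provides for collecting it.

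**Scale**

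The documents give no count of pregnancies, of patients starting strong CYP3A4 drugs, or of Sponsor decisions to stop drug in such cases. The number affected cannot be derived. What can be shown is the weight of one patient against the cohort ceilings in section 3.6:

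- Cohort 1: 1/250 = 0.4%
- Cohorts 2, 3 and 4: 1/125 = 0.8% each
- Cohort 6: 1/50 = 2%

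These are orientation only, because SAP 4.7 analyses efficacy by indication and not by cohort.

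**Endpoints not affected**

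The primary endpoint is ORR by IRC (protocol 8.1, SAP 4.3). Neither its definition nor the sample sizes in protocol 8.3 depend on follow-up after treatment ends.

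**The case against.** The strongest reply is that a site reading the whole protocol would not lose these patients. Sections 3.3, 6.4 and 7.7 all direct patients who stop treatment into LTFU, and one sentence in 9.6 is unlikely to override them. That is fair, and it means OS follow-up is put at risk, not lost outright. It does not remove the conflict: 9.6 is the section a site opens when a pregnancy occurs, and its instruction is unconditional.

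Other parts of the reply stand in full:

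- A reader might infer that pregnancy follow-up is lost. It is not. Section 9.6 requires follow-up to the end of the pregnancy, a recorded outcome, and SAE reporting where the outcome qualifies. It places the same duty on partners, who are not enrolled, so the duty does not depend on study status.
- A reader might infer that starting a strong CYP3A4 drug removes a patient from the study. It does not. The decision is made case by case with the Sponsor.
- A reader might infer that progression data are lost through this wording. Scans after stopping drug for reasons other than progression are already optional (7.3, 7.5 and Table 7-1), so little of that loss can be attributed to it.
- The undefined early termination procedures have a natural reading. Section 7.5 applies when treatment stops prematurely, and 3.3 gives all treated patients an SFU visit. What 9.6 leaves open is whether LTFU follows.
- Contraception is required (4.1), pregnancy is an exclusion (4.3), and pregnancy testing is scheduled at every cycle in Table 7-1, so few pregnancies should be expected.

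**Conclusion.** The contradiction is real and stands in the current text. Sections 9.6 and 6.3.3 say *study* where 6.4 says *treatment*, and 7.7 gives no ground for ending LTFU in either case. Taken literally, 9.6 always, and 6.3.3 when the Sponsor decides to stop drug, would end survival and subsequent-therapy follow-up that the protocol asks for elsewhere.

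The consequence is early censoring of OS, a secondary endpoint summarised descriptively by Kaplan-Meier, in what is probably a small number of patients. That number is a judgement, and a percentage loss per cohort would have no source in the documents. The study-disposition table in SAP 4.2 would show the actual number, if these reasons are recorded there as reasons for leaving the study.

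The conclusion assumes that sites apply the two sentences as written and that the patient has not withdrawn consent. It concerns the period before continued access. Section 7.9 then discontinues patients already in LTFU and limits survival collection to MTC patients, and this point does not touch that arrangement.

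**What to change.** Reconcile 9.6 and 6.3.3 with 6.4 and 7.7:

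- **Section 9.6:** state that a patient whose treatment ends because of pregnancy stays on study for EOT, SFU and LTFU (7.5 to 7.7) unless she withdraws consent. Replace the reference to early termination procedures with those named visits. Keep the existing pregnancy follow-up paragraph.
- **Section 6.3.3:** replace the clause that makes removal from the study follow from stopping drug with a statement that any patient who stops drug enters LTFU. Simply exchanging *study* for *study treatment* would be circular there, and would still not say that follow-up continues.
- **Both:** make the statement subject to 7.9 once continued access begins.

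Whether and when selpercatinib is stopped is left as it is. The cost is two short wording changes in the next amendment. No visit or procedure is added, since LTFU is already in place and may be done by phone.

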## **10. STUDY ADMINISTRATION**

### **10.1 Regulatory and Ethical Considerations**

The investigator will be responsible for reporting to the sponsor or designee significant issues related to participant safety, participant rights, or data integrity.

#### ***10.1.1 Regulatory Authority Approval***

This study will be conducted in accordance with the standard of International Conference on Harmonisation-Good Clinical Practices (ICH-GCP), an international ethical and scientific quality standard for designing, conducting, recording, and reporting studies that involve human patients. All applicable country and local regulations will also be observed. Compliance with these standards provides assurance that the rights, safety, and well-being of study patients are protected, consistent with the principles in the Declaration of Helsinki, and that the clinical study data are credible.

#### ***10.1.2 Ethics Approval***

It is the responsibility of the Investigator to ensure that the appropriate IRB/IEC has reviewed and approved this protocol prior to initiating the study. The Investigator must provide the Sponsor or Sponsor's representative with current and revised IRB/IEC membership rosters that include the members' occupations and qualifications. Sites within the US may provide a copy of the US Department of Health and Human Services Assurance Number.

The IRB/IEC must also review and approve the clinical site's ICF, other written information provided to the patient, and all advertisements that may be used for patient recruitment. The Investigator will provide the study monitor with copies of these documents and of dated IRB/IEC approval(s) prior to the start of the study.

If the protocol or the ICF is amended during the study, the Investigator is responsible for ensuring that the IRB/IEC has reviewed and approved these amended documents. Approval of the amended documents must be obtained from the IRB/IEC before implementation and before new patients are consented to participate in the study using the amended version of the ICF. The Investigator must provide the Sponsor with the dated IRB/IEC approval of the amended documents as soon as available.

#### ***10.1.3 Patient Informed Consent***

Prior to study entry, the Investigator or designee will explain the nature, purpose, benefits, and risks of participation in the study to each patient, patient's legally acceptable representative, or impartial witness. Written informed consent must be obtained prior to the patient entering the study (before initiation of any study-related screening procedure). Sufficient time will be allowed to discuss any questions raised by the patient. The ICF, which will contain all US federally-required elements, all International Conference on Harmonisation (ICH)-required elements, and

Health Insurance Portability and Accountability Act authorization information in a language that is understandable to the patient, must be signed by all patients. The process of obtaining consent will be in compliance with all applicable local and country regulations and ICH requirements.

If the ICF is amended during the study, the Investigator must follow all applicable regulatory requirements pertaining to IRB/IEC approval of the amended form. The clinical site must use the amended ICF for all new patients and must re-consent any ongoing patients with the amended ICF, if instructed to do so by the IRB/IEC.

The sample ICF prepared by the Sponsor may be found in the Study Manual. The consent and re-consenting process should be properly documented in the source documentation.

#### **10.1.4      *Serious Adverse Event Notification to the Institutional Review Board/Independent Ethics Committee***

Suspected unexpected serious adverse reactions (SUSARs) will be reported to the IRB/IEC according to their institutional policy by the Investigator or Sponsor (or Sponsor designee) according to country requirements. Copies of each report and documentation of IRB/IEC notification and acknowledgement of receipt will be kept in the Investigator's study file.

